7.4 Protocol Amendments

Any amendments to the study protocol which may affect the conduct of the study or the potential safety of or benefits to participants (e.g., changes to the study objectives, study design, sample size, or study procedures) will require a formal amendment to the protocol. Any protocol amendments will be approved by the Principal Investigators and will require approval by the University of California IRB, the Tanzania NIMR, and the funders (as needed). Administrative changes (e.g., minor corrections or clarifications that have no effect on the way the study is conducted) will not need to undergo a formal amendment process.

7.5 Adverse Event Reporting and Definitions

7.5.1 Adverse Event (AE)

An adverse event (AE) is the development of an undesirable medical condition or the deterioration of a pre-existing medical condition (not relevant in this study). AE's will be collected by means of a standard question on the follow-up questionnaire: "Have you developed any new health problems since the previous visit?" AE's will be recorded at every visit.

Spontaneously reported AE's and/or observed AE's will be recorded on a separate Adverse Events form with information about (1) date of onset and date of recovery, (2) seriousness, (3) severity and (4) outcome.

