4.6.2 Overview of Data Collection Instruments

Data will be collected in the schedule described in section 4.4 Schedule of Events, and includes:

- Baseline patient data includes demographic information, such as age, gender, medical history, and injury characteristics.
- The EuroQol-5 Dimensions, 3-level questionnaire (EQ-5D)²⁰, Swahili version, which is a validated instrument for measuring patient quality of life.
- The Function Index for Trauma (FIX-IT)²¹, a validated instrument for evaluating healing in lower-extremity fractures. The scoring system includes a single-leg stand, ambulation, and palpation test.
- The Modified Radiographic Union Score for Tibia (mRUST)²² is a validated, radiographic measure of bony union.

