7.5.2 Serious Adverse Event (SAE)

A **Serious** Adverse Event is an adverse event occurring during any phase of the study, which fulfills one or more of the following criteria:

1. Results in death;
2. Is immediately life-threatening or requires in-subject hospitalization;

3. Results in persistent or significant disability or incapacity.

The causality of Serious Adverse Events (i.e. the relationship to study treatment) will be assessed by the DSMC, who in completing the relevant REDCAP form must answer ‘yes’ or ‘no’ to the question “Is there a reasonable possibility that the event may have been caused by the local Gentamicin injection?”

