7.5.3 Safety Monitoring

The following factors should be considered when deciding if there is a “reasonable possibility” that an Adverse Event may have been caused by the investigational product.

- Time course of events and exposure to drug – did the AE occur in a reasonable temporal relationship to the administration of the intervention?
- No alternative cause - the AE cannot be reasonably explained by another etiology such as an underlying disease (not previously present), other drugs, or environmental factors.

There would not be a “reasonable possibility” of causality if none of the above criteria apply or where there is evidence of exposure and a reasonable time course, but there is another more likely cause of the AE.

The subjects will additionally be asked to assess the **severity** of each reported Adverse Event according to the following scale:

Mild	= awareness of sign or symptom, but easily tolerated
Moderate	= discomfort sufficient to cause interference with normal activities
Severe	= incapacitating, with inability to perform normal activities.

Subjects will again be asked about the seriousness and severity of previously reported adverse events at subsequent follow-up visits, in order to track **outcome**.

Adverse Events believed to be secondary to intervention or standard of care with “reasonable probability” will be reviewed at interim analyses, and reported by the DSMC at that time to all required parties.

The Data and Safety Monitoring Committee (DSMC) for the study will consist of orthopedic surgeon [name] (Minneapolis, MN, USA), emergency medicine physician [name] (Dar es Salaam, Tanzania), and health services researcher [name] (Baltimore, MD, USA). [name] [name] will serve as the committee chair.

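### The AE definition can be read as leaving out worsening of pre-existing conditions, and the SAE criteria omit a prolonged stay although participants are already inpatients when injected

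*Combined protocol and SAP*

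**What the plan says.** Section 7.5.1 (Adverse Event) has two limbs: the appearance of an undesirable condition, or "the deterioration of a pre-existing medical condition (not relevant in this study"). Events are solicited with one standard question on the follow-up questionnaire: "Have you developed any new health problems since the previous visit"? Events that participants volunteer or staff notice go on a separate form.

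Section 7.5.2 (Serious Adverse Event) defines an SAE as an AE that meets at least one of three criteria. The first is death and the third is lasting or significant disability. The second reads "Is immediately life-threatening or requires in-subject hospitalization". The section then states: "The causality of Serious Adverse Events (i.e. the relationship to study treatment) will be assessed by the DSMC". The DSMC answers yes or no on whether the local gentamicin injection could reasonably have caused the event.

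Section 7.5.4 (Stopping Guidelines) leaves termination for harm to the DSMC's judgment over several endpoints. SAEs are the only one it names.

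**The concern.** Two gaps appear when the definitions are applied as written.

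- **Worsening of an existing illness.** The bracketed remark in Section 7.5.1 appears to switch off the second limb of the AE definition, and the scripted question points the same way. Because every SAE must first be an AE, whatever the AE definition leaves out is also left out of the SAE class.
- **A longer index stay.** A hospitalization criterion without prolongation works for someone at home. It works poorly for someone already on the ward, and that is where participants are in the period closest to exposure.

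What is at stake is classification. An event outside the AE class, or classed as non-serious, is not clearly put to the DSMC's causality question and is not counted in the endpoint that Section 7.5.4 names.

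**Working it through.** No formula applies, and the plan states no figure on this point to reproduce. The check is to set the passages side by side.

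**Step 1. Can participants have a pre-existing condition that worsens?** Yes.
- Table 1 (Section 4.2) lists 11 exclusions. None names kidney disease, diabetes or a similar chronic illness.
- Section 4.6.2 (Overview of Data Collection Instruments) says "Baseline patient data includes demographic information, such as age, gender, medical history, and injury characteristics", and Section 4.4 also lists medical history at baseline. The plan therefore expects some history to record.
- Section 4.4 judges day-2 creatinine against the participant's own baseline, so the protocol itself looks for deterioration from a starting value.

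The plan thus does not make deterioration of an existing condition impossible, which is what the bracketed remark would need in order to be harmless.

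**Step 2. Does another part of the AE text bring such worsening back in?** Not clearly. The scripted question asks about new problems. The separate form takes volunteered and observed events, but these are still AEs under the same definition.

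**Step 3. Are participants inpatients when exposed?** Yes. Section 4.3 recruits from patients admitted to the hospital and randomizes them during surgery once closure is complete. Section 4.7.2 (Study Solution Administration) places the injection directly after closure. Section 4.4 then has them moved to the ward.

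**Step 4. Is prolongation covered anywhere?** The visible text does not mention it.

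**Step 5. Apply the literal wording to example events.**

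| Example event | AE? | SAE? | DSMC causality question? |
|---|---|---|---|
| New complication after discharge that leads to readmission | Yes | Yes | Yes |
| New in-hospital complication that is immediately life-threatening | Yes | Yes | Yes |
| New in-hospital complication that only lengthens the index stay | Yes | Not clearly | Not clearly |
| Worsening of an illness present before the injury | No, if the bracket is literal | No, because it is not an AE | No |

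The first and third rows could be the same clinical event. Whether it is serious then depends on whether it occurs before or after discharge.

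**Size.** The documents give no rate for events of the third or fourth kind, so an expected number of lost or misclassified events cannot be calculated.

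**The case against.** The strongest reply is that both phrases have a milder reading. Section 7.5.1 does keep deterioration in its sentence, so the bracket may record only that no such cases are expected. An acute complication in someone with chronic disease may also count as a newly developed condition. Likewise, an event needing inpatient care may be said to require hospitalization even if the patient is already in a bed. These readings are reasonable, but the text does not choose between them, and different staff could apply it differently.

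The second reply is that there are other routes to review. Volunteered and observed AEs are recorded (Section 7.5.1). Deaths and complications requiring reoperation go to the Steering Committee (Section 4.7.3). AEs believed to be related "will be reviewed at interim analyses, and reported by the DSMC at that time to all required parties" (Section 7.5.3). The DSMC may require further analyses (Section 7.5.4). This stands and narrows the gap mainly to non-fatal events that need no reoperation. It does not close the gap: the Steering Committee's votes concern the need for reoperation and whether the event is a primary outcome, not whether the injection caused it.

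A reader might go further and infer that nobody judges causality for non-serious AEs, or that creatinine rises will go unreported. The documents do not support that. The four items in Section 7.5.1 ("1) date of onset and date of recovery, (2) seriousness, (3) severity and (4) outcome") are a summary, and the forms, any DSMC charter and any separate procedures document are not shown. Section 7.5.3 gives causality factors for AEs in general. Creatinine is scheduled before surgery and on day 2 for participants in both arms, whatever the AE label. Clarifying these two matters is optional and not part of this point.

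**Conclusion.** The point holds as a defect of wording. Taken literally, Section 7.5.1 leaves worsening of a pre-existing condition out of AEs, and hence out of SAEs. Section 7.5.2 does not settle whether an early complication that only prolongs the index stay is serious.

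The conclusion rests on the visible text being what site staff work from; form instructions that are not shown could already resolve it. The effect cannot be sized. Putting assumed event rates through 50 participants per arm would give the chance of an event at those rates, not how often this wording loses one.

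It would be wrong to infer that harms go unseen or that the trial's results are compromised. The feasibility and efficacy analyses do not depend on these definitions. The correction should still be made: it is cheap, it concerns the safety record, and the pilot is meant to test procedures for a definitive trial provisionally sized at 890 patients (Section 5.1).

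**What to change.** Make three edits:

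1. In Section 7.5.1, delete the bracketed remark after the second limb of the AE definition.
2. In the scripted question, ask about *new or worsened health problems*.
3. In Section 7.5.2, change the hospitalization part of the second criterion to *requires or prolongs inpatient hospitalization*.

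These edits change no test, treatment or care rule.

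The cost is a formal amendment under Section 7.4, since safety reporting is affected, with approval by the principal investigators, both ethics bodies and the funders as needed. The follow-up form wording changes, and there will be a few more AE and SAE reports to process. If recruitment has begun, record the date of the change so that counts made under the two wordings can be told apart.

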7.5.2 Serious Adverse Event (SAE)

A **Serious** Adverse Event is an adverse event occurring during any phase of the study, which fulfills one or more of the following criteria:

1. Results in death;
2. Is immediately life-threatening or requires in-subject hospitalization;

3. Results in persistent or significant disability or incapacity.

The causality of Serious Adverse Events (i.e. the relationship to study treatment) will be assessed by the DSMC, who in completing the relevant REDCAP form must answer ‘yes’ or ‘no’ to the question “Is there a reasonable possibility that the event may have been caused by the local Gentamicin injection?”

7.5.3 Safety Monitoring

The following factors should be considered when deciding if there is a “reasonable possibility” that an Adverse Event may have been caused by the investigational product.

- Time course of events and exposure to drug – did the AE occur in a reasonable temporal relationship to the administration of the intervention?
- No alternative cause - the AE cannot be reasonably explained by another etiology such as an underlying disease (not previously present), other drugs, or environmental factors.

There would not be a “reasonable possibility” of causality if none of the above criteria apply or where there is evidence of exposure and a reasonable time course, but there is another more likely cause of the AE.

The subjects will additionally be asked to assess the **severity** of each reported Adverse Event according to the following scale:

Mild	= awareness of sign or symptom, but easily tolerated
Moderate	= discomfort sufficient to cause interference with normal activities
Severe	= incapacitating, with inability to perform normal activities.

Subjects will again be asked about the seriousness and severity of previously reported adverse events at subsequent follow-up visits, in order to track **outcome**.

Adverse Events believed to be secondary to intervention or standard of care with “reasonable probability” will be reviewed at interim analyses, and reported by the DSMC at that time to all required parties.

The Data and Safety Monitoring Committee (DSMC) for the study will consist of orthopedic surgeon [name] (Minneapolis, MN, USA), emergency medicine physician [name] (Dar es Salaam, Tanzania), and health services researcher [name] (Baltimore, MD, USA). [name] [name] will serve as the committee chair.

7.5.4 Stopping Guidelines

The trial may be terminated for reasons of harm at the judgment of the DSMC. Several endpoints will be examined, including serious adverse events as described in the protocol. While the analysis would consider mal-distribution of predictive factors such as age, it is recognized that ethical considerations require careful considerations of statistical tests as well as qualitative

judgments in the light of experience. Any additional analyses required by the DSMC will be reported as needed.

7.5 Dissemination Policy

At the conclusion of the study there will be a principal manuscript reporting the findings of the feasibility trial primary study endpoints. This data will be used to inform the definitive trial.

